## **12.0 VISUAL FUNCTION QUESTIONNAIRE**

National Eye Institute Visual Function Questionnaire responses collected at Baseline will not be summarized as part of this SAP.

## **13.0 INTERIM ANALYSES**

No interim analysis is currently planned for the study.

Two database locks are planned for this study as described in [Section 5.1](#):

- 1) When all patients have completed Week 24 visit or have prematurely discontinued before Week 24 visit (primary lock), and
- 2) When all patients have completed the Week 52 visit or exited the study.

The analysis results based on the first database lock is considered as the primary analysis. The analyses based on the second database lock will provide further efficacy and safety information. Two CSRs will be written, one following each lock.

## **14.0 DETERMINATION OF SAMPLE SIZE**

The sample size calculation is based on paired-eye differences using a normal approximation with a 2-sided significance level of 0.05, assuming that there is no difference in mean IOP change from baseline between Bim SR eyes and SLT eyes, and that change from baseline in IOP has a standard deviation of 4 mmHg. A sample size of 144 patients will provide approximately 98% power in showing noninferiority in 3 out of 3 timepoints with a noninferiority margin of 1.5 mmHg, and 90% power in showing noninferiority in 2 out of 3 timepoints with a noninferiority margin of 1.0 mmHg, assuming that both the between-eyes and the within-patient correlation coefficients are 0.5.

Assuming a premature discontinuation rate of 10%, approximately 160 patients are to be enrolled into this study.

## **15.0 STATISTICAL SOFTWARE**

Statistical analyses will be performed using version 9.3 (or newer) of SAS software.

## **16.0 DATA HANDLING CONVENTIONS**

### **16.1 EFFICACY DATA**

As stated in protocol [Section 5.9.1.5](#) Retreatment with Bim SR, when eye(s) received non-study IOP lowering medication or procedure, to avoid confounding of efficacy data, IOP measurements obtained after initiating the use of non-study IOP-lowering medication or procedure in an eye will be treated as missing for that eye.

Additionally, handling of missing data will be supplemented by sensitivity analyses using multiple imputation and tipping point (adding different penalties on the imputed values) approach.

### **16.2 VISIT TIME WINDOWS**

[Table 16-1](#), [Table 16-2](#), and [Table 16-3](#) present respectively, the analysis visits assigned for efficacy and safety assessments for patients who received only Cycle 1 implant, Cycles 1 and 2 implants and Cycles 1, 2, and 3 implants. If multiple assessments were taken within an analysis window, the assessment obtained on the day closest to the target day will be used; in the case of a tie, the assessment obtained on the later day will be used in the analysis. Please be noted, IOP values will be measured for safety, and these safety IOP values should not be included in efficacy analysis of IOP. IOP values for safety are often recorded on unscheduled IOP eCRF page with assessment reason provided in free text, which cannot be programmed straightforwardly. For simplicity, an unscheduled IOP values in an analysis windows will not be used, unless the IOP value is the only one in the window.

**Table 16-1 Visit Windows for Patients who only had Bim SR Cycle 1 Implant**

Derived Visit	Target Visit Day	Visit Window
Baseline a	-1	≤ (SLT Date -1)
SLT/Sham SLT Administration Day 1	1	SLT Date
Bim SR Cycle 1 Day 1 b	Bim SR Cycle 1 Day 1	Bim SR Cycle 1 Day 1
Bim SR Cycle 1 Day 2 b	Bim SR Cycle 1 Day 1 + 1	Bim SR Cycle 1 Day 1 + 1
Week 4/Cycle 1 Week 4 b	25	[Bim SR Cycle 1 Day 1+ 2, 38]
Week 8/Cycle 1 Week 8 b	53	[39, 66]
Week 12/Cycle 1 Week 12 b	81	[67, 91]
Week 15/Cycle 1 Week 15 b	102	[92, 105]
Week 16/Cycle 1 Week 16 b	109	[106, 122]
Week 20/Cycle 1 Week 20 b	137	[123, 150]
Week 24/Cycle 1 Week 24 b	165	[151, 178]
Week 28/Cycle 1 Week 28 b	193	[179, 203]
Week 31/Cycle 1 Week 31 b	214	[204, 217]
Week 32/Cycle 1 Week 32 b	221	[218, 234]
Week 36/Cycle 1 Week 36 b	249	[235, 262]
Week 40/Cycle 1 Week 40 b	277	[263, 290]
Week 44/Cycle 1 Week 44 b	305	[291, 315]
Week 47/Cycle 1 Week 47 b	326	[316, 343]
Week 52/Cycle 1 Week 52 b	361	>=344

a Relative to the date of the SLT treatment.

b Relative to the date of Bim SR 1st implant. If a patient did not receive the first Bim SR cycle, but treated in SLT at Day 1, Bim SR cycle 1 Day 1 will be determined as SLT+ 3 days.

**Table 16-2 Visit windows for patients who only had Bim SR Cycles 1 and 2 implants**

Derived Visit	Target Visit Day	Visit Window
Baseline a	-1	≤ (SLT Date -1)
SLT/Sham SLT Administration Day 1	1	SLT Date
Bim SR Cycle 1 Day 1 b	Bim SR Cycle 1 Day 1	Bim SR Cycle 1 Day 1
Bim SR Cycle 1 Day 2 b	Bim SR Cycle 1 Day 1 + 1	Bim SR Cycle 1 Day 1 + 1
Week 4/Cycle 1 Week 4 b	25	[Bim SR Cycle 1 Day 1+ 2, 38]
Week 8/Cycle 1 Week 8 b	53	[39, 66]
Week 12/Cycle 1 Week 12 b	81	[67, 91]
Week 15/Cycle 1 Week 15 b	102	[92, Bim SR Cycle 2 Day1-Bim SR Cycle 1 Day 1]
Week 16/Bim SR Cycle 2 Day 1 c	1	Bim SR Cycle 2 Day 1
Cycle 2 Day 2 c	2	Bim SR Cycle 2 Day 1 + 1
Week 20/Cycle 2 Week 4 c	29	[Bim SR Cycle 2 Day 1+ 2, 42]
Week 24/Cycle 2 Week 8 c	57	[43, 70]
Week 28/Cycle 2 Week 12 c	85	[71, 95]
Week 31/Cycle 2 Week 15 c	106	[96, 109]
Week 32/Cycle 2 Week 16 c	113	[110, 126]
Week 36/Cycle 2 Week 20 c	141	[127, 154]
Week 40/Cycle 2 Week 24 c	169	[155, 182]
Week 44/Cycle 2 Week 28 c	197	[183, 207]
Week 47/Cycle 2 Week 31 c	218	[208, 235]
Week 52/Cycle 2 Week 36 c	253	>=236

a Relative to the date of the SLT treatment.

b Relative to the date of Bim SR 1st implant. If a patient did not receive the first Bim SR cycle, but treated in SLT at Day 1, Bim SR cycle 1 Day 1 will be determined as SLT+ 3 days.

c Relative to the date of Bim SR 2nd implant.

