Table 5 Administration Cycle 3 Schedule of Visits and Procedures (Stage 1 Patients Only)

	Bimatoprost SR Cycle 3 Day 1 Administration	Cycle 3 Day 2 Safety Visit	Cycle 3 Day 4 Phone Call ^a	Cycle 3 Week 2 Phone Call ^a
Visits	Week 32			
Visit Windows	-2/+4 days			
Adverse Events	X	X	X	X
Concomitant Medications/Procedures	X	X	X	X
Vital Signs (at rest ≥ 5 minutes)	X	X		
Pregnancy Test				
Ocular Examinations in bold should be performed in the order shown				
Pre-Hour 0 Exams (may perform in any order before Hour 0 IOP)				
Macroscopic Conjunctival Hyperemia Assessment ^b		OU		
Best-Corrected Visual Acuity ^c		OU		
Intraocular Pressure H0	SC/T ^d	OU		
Non-contact Exams (may perform in any order at any time before gonioscopy)				
Macroscopic Iris Color Assessment				
Manifest Refraction ^c				
Visual Field ^e				
Specular Microscopy				
				
Biomicroscopy ^b	SC/T ^d	OU		

	Bimatoprost SR Cycle 3 Day 1 Administration	Cycle 3 Day 2 Safety Visit	Cycle 3 Day 4 Phone Call ^a	Cycle 3 Week 2 Phone Call ^a
Visits	Week 32			
Visit Windows	-2/+4 days			
Gonioscopy/Angle Assessment				
Pachymetry (may be done any time after gonioscopy)				
Pupil Dilation (perform post-dilation eye exams in any order)				
Dilated Ophthalmoscopy				
Optic Disc Examination				
Contact Interactive Response System ^f	X			
Treatment and/or Sham Administration ^b	X			

H = Hour; Hour 0 = 08:00 ± 1 hour; IOP = intraocular pressure; OU = both eyes; SC/T = applies to only patients with sickle cell disease or trait or other hemoglobinopathies; X = perform procedure

^a If the patient reports symptoms or findings of concern in the Day 4 or Week 2 phone call (including but not limited to photophobia, blurred vision, eye pain, vitreous floaters), the investigator must bring the patient in for ophthalmic examination.

^b [REDACTED] See Procedure Manual for details.

^c Manifest refraction will be used to provide a correction for best-corrected visual acuity testing. At all study visits, if there is a 2-line or more reduction in visual acuity from the last best-corrected visual acuity performed, a repeat manifest refraction in both eyes and best-corrected visual acuity will be performed.

^d Optional biomicroscopy and IOP measurement in both eyes may be performed 4 hours after study treatment for patients with sickle cell/trait or other hemoglobinopathies.

^e For a given patient, the same test methodology must be used for historical fields and all fields performed throughout the study.

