8.4.3.5 Cycle 1: Day 4 and Week 2 (Cycle 1 Phone Calls)

On Cycle 1 Day 4 and Cycle 1 Week 2, the patient will be contacted by telephone to collect the following:

- Collection of adverse events
- Collection of concomitant medications and procedures

If the patient reports symptoms or findings of concern in the Day 4 or Week 2 phone call (including but not limited to photophobia, blurred vision, eye pain, vitreous floaters), the investigator must bring the patient in for ophthalmic examination.

8.4.3.6 Cycle 1: Weeks 4, 8, 12, and 15

The following procedures are performed at Weeks 4 (\pm 4 days), 8 (\pm 4 days), 12 (\pm 4 days), and 15 (\pm 4 days):

- Collection of adverse events
- Collection of concomitant medications and procedures
- Vital signs (at rest \geq 5 minutes)

The following procedures should be performed in both eyes (procedures in bold should be done in the order shown):

- **Pre-Hour 0 examinations** (may be performed in any order before Hour 0 IOP):
 - Macroscopic conjunctival hyperemia assessment (The examination may also include, [REDACTED])
 - Best-corrected visual acuity
- **Intraocular pressure measurement at Hour 0**
- **Non-contact examinations:** The following may be performed in any order, at any time before gonioscopy (including prior to Hour 0 IOP):
 - Macroscopic iris color assessment (Weeks 4 and 12 only)
 - Manifest refraction (Week 12 only)
 - Specular microscopy (Weeks 4 and 12 only)
 - Biomicroscopy (The examination may also include, [REDACTED])
- **Intraocular pressure measurement at Hours 2 and 8** (at selected sites in consenting patients; Week 12 only)
- **Gonioscopy/angle assessment** (The examination will also include, [REDACTED]). Perform gonioscopy at least 2 hours prior to H8 IOP measurement at Week 12.)
- Pachymetry (may be done any time after gonioscopy; Weeks 4 and 12 only)
- **Pupil dilation** (Week 12 only) (post dilation examinations below may be performed in any order)
 - Dilated ophthalmoscopy (Week 12 only)
 - Optic disc examination (Week 12 only)

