8.4.3.7 Week 16 (Bimatoprost SR Cycle 2 Day 1 Administration)

With the implementation of Amendment 3, patients who are enrolled and have not yet reached Week 16 will not receive Cycle 2 administration and will be followed for the duration of the study through the Week 52/Exit visit. Therefore, the Week 16 will not be required for these patients.

The following procedures are performed at Week 16 (-2/+4 days):

- Collection of adverse events
- Collection of concomitant medications and procedures
- Vital signs (at rest \geq 5 minutes)
- Contact interactive response system for kit allocation (this contact may take place 1 day prior to the Cycle 2 administration day, if needed)
- Administer assigned study treatment
- Contact interactive response system to confirm kit assignment if applicable

All patients must remain at the surgical facility for bilateral eye examination at least 1 hour after Bimatoprost SR administration or sham administration procedure. For patients with sickle cell disease or trait (or other hemoglobinopathies), the investigator may perform optional biomicroscopy and measure IOP in both eyes 4 hours after the administration procedure as desired. This IOP examination is for postoperative purposes only, and as such does not require a masked, 2-person reading method. The IOP should be taken only once to avoid excessive postadministration (or sham administration) manipulation of the eye, and should be taken by the investigator (or other unmasked, qualified personnel). This postadministration (or sham administration) examination may be performed using a Goldmann applanation tonometer or a hand-held tonometer. See full procedure instructions in the Procedure Manual.

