8.4.3.9 Cycle 2: Day 4 and Week 2 (Cycle 2 Phone Calls)

These phone calls are not required if Cycle 2 is not received.

On Cycle 2 Day 4 and Cycle 2 Week 2, the patient will be contacted by telephone to collect the following:

- Collection of adverse events
- Collection of concomitant medications and procedures

If the patient reports symptoms or findings of concern in the Day 4 or Week 2 phone call (including but not limited to photophobia, blurred vision, eye pain, vitreous floaters), the investigator must bring the patient in for ophthalmic examination.

8.4.3.10 Cycle 2: Weeks 20, 24, 28, and 31

The following procedures are performed at Weeks 20 (± 4 days), 24 (± 4 days), 28 (± 4 days), and 31 (± 4 days):

- Collection of adverse events
- Collection of concomitant medications and procedures
- Vital signs (at rest ≥ 5 minutes)

The following procedures should be performed in both eyes (procedures in bold should be done in the order shown):

- **Pre-Hour 0 examinations:**
 - Macroscopic conjunctival hyperemia assessment (The examination may also include, [REDACTED])
 - Best-corrected visual acuity
- **Intraocular pressure measurement at Hour 0**
- **Non-contact examinations:** The following may be performed in any order, at any time before gonioscopy (including prior to Hour 0 IOP):
 - Macroscopic iris color assessment (Week 24 only)
 - Manifest refraction (Week 24 only)
 - Visual field (If dilation is required to perform this test, then the visual field test should be performed after the last IOP measurement of the day.) (Week 24 only)
 - Specular microscopy (Week 24 only)
 - Biomicroscopy (The examination may also include, [REDACTED])
- **Intraocular pressure measurement at Hours 2 and 8** (at selected sites in consenting patients; Week 24 only)
- **Gonioscopy/angle assessment** (The examination will also include, [REDACTED])
- Pachymetry (Week 24 only) (may be done any time after gonioscopy)
- Pupil dilation (may perform post-dilation eye exams in any order; Week 24 only)
 - Dilated ophthalmoscopy (Week 24 only)
 - Optic disc examination (Week 24 only)

8.4.3.11 For Stage 1 Patients Only: Week 32 (Bimatoprost SR Cycle 3 Day 1 Administration)

The following procedures are performed at Week 32 (-2/+4 days):

- Collection of adverse events
- Collection of concomitant medications and procedures

- Vital signs (at rest \geq 5 minutes)

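### SAP Tables 16-1 and 16-2 end the Week 15 and Week 31 windows at target +3 days although the protocol allows +4, so a reading on the last permitted day is relabelled Week 16 or Week 32

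*SAP*

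**What the plan says.** **Visit tolerance.** Protocol Section 8.4.3.10 sets the later Cycle 2 visits at "28 (± 4 days), and 31 (± 4 days"). Section 8.4.3.6 gives Week 15 the same tolerance of 4 days either way.

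**Analysis windows.** SAP Section 16.2 assigns each assessment to a visit by day range, with one table per number of implants received. Table 16-1 has a row "Week 16/Cycle 1 Week 16" after Week 15 and a Week 32 row after Week 31. Table 16-2 has a row "Week 32/Cycle 2 Week 16" after Week 31, but its Week 15 window is "92, Bim SR Cycle 2 Day1-Bim SR Cycle 1 Day 1", so it stays open until the second implant. When several assessments share a window, the one nearest the target day is taken.

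**What happens at Weeks 16 and 32.** These are administration visits. For patients who had not reached Week 16 when Amendment 3 took effect, Protocol Section 8.4.3.7 says: "Therefore, the Week 16 will not be required for these patients". Week 32 procedures are in Protocol Table 5, "Administration Cycle 3 Schedule of Visits and Procedures (Stage 1 Patients Only"). On an administration day the only post-procedure IOP is an optional one in patients with hemoglobinopathies, and Section 8.4.3.7 adds: "This IOP examination is for postoperative purposes only".

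**Where the values are used.** SAP Section 10.2 summarises IOP change at Weeks 8, 15 and 20, and the percentage of eyes with at least a 20% reduction at each post-baseline visit. Section 10.4 uses Week 15 in the multiple imputation for the tipping-point analysis.

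**The concern.** An analysis window should hold every reading that the protocol accepts for that visit. Here a visit made exactly 4 days late is compliant, yet its IOP is filed under a label that has no scheduled efficacy reading. The nearest-to-target rule chooses only among readings already inside a window, so it cannot bring the value back.

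Three outputs could be touched: the Week 15 secondary IOP summary for one-implant patients; the responder percentage at Week 15 (one implant) and Week 31 (one or two implants); and the Week 15 input to the imputation, for any one-implant patients who stay in the mITT population.

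There is also a side effect. Section 16.2 uses an unscheduled IOP when it is the only one in its window. A window with no scheduled IOP is where that is most likely, so stray readings could appear as Week 16 or Week 32 efficacy data.

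**Working it through.** **1. Inputs.** Days in Table 16-1 count from the first implant. The Week 31 to Week 36 rows of Table 16-2 count from the second. Tolerances come from Protocol Sections 8.4.3.6, 8.4.3.7 and 8.4.3.10 and Protocol Table 3.

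| SAP table, visit | Target | Window | Next row | Next target | Next window |
|---|---|---|---|---|---|
| 16-1, Week 15 | 102 | 92 to 105 | Week 16 | 109 | 106 to 122 |
| 16-1, Week 31 | 214 | 204 to 217 | Week 32 | 221 | 218 to 234 |
| 16-2, Week 31 | 106 | 96 to 109 | Week 32 | 113 | 110 to 126 |

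**2. Reproducing the bounds.** Section 16.2 states no rule, but the fixed bounds lie at the midpoint of adjacent targets, with an exact midpoint going to the later visit:
- (102 + 109)/2 = 105.5, so Week 15 ends at 105.
- (214 + 221)/2 = 217.5, so Week 31 ends at 217.
- (106 + 113)/2 = 109.5, so Week 31 in Table 16-2 ends at 109.
- (109 + 137)/2 = 123, so Week 16 ends at 122.

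The same pattern reproduces all the fixed midpoint bounds checked in Tables 16-1, 16-2 and 16-3. The tables are internally consistent. The short windows come from the extra rows.

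**3. Protocol tolerance against the windows, at the SAP targets.**
- Table 16-1, Week 15: 102 + 4 = 106 > 105, labelled Week 16.
- Table 16-1, Week 31: 214 + 4 = 218 > 217, labelled Week 32.
- Table 16-2, Week 31: 106 + 4 = 110 > 109, labelled Week 32.

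Offsets -4 to +3 stay in place, so 1 of 9 permitted days moves. No other ±4-day visit with fixed bounds loses a day in any of the three tables. For the primary visits, Week 12 at 81 ± 4 is 77 to 85, inside 67 to 91. Week 24 at 165 ± 4 or 57 ± 4 lies inside 151 to 178 or 43 to 70.

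**4. Allowing for implant timing.** Let v be the visit offset (-4 to +4).
- *Two implants, Week 31 timed from Day 1.* Cycle 2 is given c = -2 to +4 days from schedule, so the relative day is 106 + v - c, running from 98 to 112. It passes 109 when v - c ≥ 4: three values of v at c = -2, two at c = -1, one at c = 0 and none later. That is 6 of 9 × 7 = 63, or 9.5%.
- *Two implants, timed from the second implant.* 1 of 9, or 11%.
- *One implant, given o = 0 to 3 days after Day 4.* The relative day is 102 + v - o (or 214 + v - o), and it is lost only at v = 4, o = 0. That is 1 of 9 × 4 = 36, or 2.8%.

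The documents do not fix the scheduling anchor or the day count, and this moves the one-implant figure. Counting Week 15 as SLT + 105 days with a Day 4 implant as day 1 gives day 103, so +3 and +4 are lost. A Day 7 implant gives day 100, so none is lost. Timing from the implant itself gives day 106, so 0 to +4 are lost.

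**5. Bounds without the extra rows, same midpoint pattern.**
- Table 16-1: (102 + 137)/2 = 119.5 and (214 + 249)/2 = 231.5.
- Table 16-2: (106 + 141)/2 = 123.5.

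Table 16-3 already does this. Its Week 47 has target 106 and the next target is 141, with no row between, and its window is 96 to 123.

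**The case against.** The strongest reply is that the Week 16 and Week 32 rows are not empty. The tables sort patients by implants received, not by stage or amendment. Under Protocol Section 4.5.2 a patient given nonstudy topical treatment in the Bimatoprost SR eye only still attends the administration visits and receives sham in that eye. Only patients treated in both eyes skip them. Such patients may also attend the following Day 2 safety visit, which has a scheduled Hour 0 IOP. Section 8.4.3.8 waives that visit when Cycle 2 is not received, so the two sections need to be reconciled.

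This stands, and it has a consequence for the repair. At the SAP targets a Cycle 2 sham falls on days 107 to 113 (109 - 2 to 109 + 4), so its Day 2 reading falls on days 108 to 114. That is inside a Week 15 window widened to 119. A real Week 15 reading would be nearer the target and would win. If it were missing, the post-sham value would replace it, including in an SLT eye whose IOP is not excluded for rescue.

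It does not rescue the present bounds. The administration visit itself has no scheduled efficacy IOP, and Amendment 3 patients who had not reached Week 16 have neither visit.

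The reply is also right about size. A reader might infer that any late reading is relabelled, or that Week 15 is damaged throughout. At the SAP targets only day +4 moves, and in Tables 16-2 and 16-3 Week 15 runs up to the second implant. The affected secondary summaries are descriptive, Week 31 is not one of the named secondary IOP visits, and Protocol Section 8.8 asks sites to schedule close to the specified day. In the responder table the value moves to another label and is not deleted.

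A smaller repair, ending each window at target +4, would cover step 3. It would still lose 3 of the 63 combinations (v - c ≥ 5: two at c = -2, one at c = -1).

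**Conclusion.** The point holds as a minor mismatch. Three analysis windows end one day before the protocol's tolerance does, and an on-protocol reading on day 106 or 218 (Table 16-1) or day 110 (Table 16-2) is filed under a visit with no scheduled efficacy IOP.

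The share of permitted days or day combinations affected is 11% at the SAP targets, 9.5% for two implants timed from Day 1, and 2.8% for one implant spread over Day 4 to Day 7. All three assume evenly spread visit days. Clustering near the target would lower them, and a different day count could raise or remove the one-implant figure.

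A reader might infer that the noninferiority result is at risk. The documents do not support that: the Week 4, 12 and 24 windows hold every permitted day. The only route towards the analyses of the primary variable is the Week 15 input to the tipping-point imputation, for the few one-implant patients who could remain in mITT. It is worth correcting because Week 15 is a named secondary visit and the change is nearly free.

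**What to change.** For IOP, remove the Week 16 and Week 32 rows from Table 16-1 and the Week 32 row from Table 16-2, then reset the adjoining bounds:

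| SAP table | Visit | New window |
|---|---|---|
| 16-1 | Week 15 | 92 to 119 |
| 16-1 | Week 20 | 120 to 150 |
| 16-1 | Week 31 | 204 to 231 |
| 16-1 | Week 36 | 232 to 262 |
| 16-2 | Week 31 | 96 to 123 |
| 16-2 | Week 36 | 124 to 154 |

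The rows can stay for other assessments made on administration days.

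Add one line to Section 16.2: in patients who did not receive the implant of that cycle, IOP taken on or just after a sham administration day, including the Cycle 2 or Cycle 3 Day 2 safety visit, cannot supply the Week 15 or Week 31 efficacy value. It would also help to state the midpoint pattern and the day count in words.

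The cost is two table edits and one exclusion line, made before the applicable database lock. No new data are needed and no primary window changes.

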**Table 16-3 Visit windows for patients who had Bim SR Cycle 1, 2 and 3 implants**

Derived Visit	Target Visit Day	Visit Window
Baseline a	-1	≤ (SLT Date -1)
SLT/Sham SLT Administration Day 1	1	SLT Date
Bim SR Cycle 1 Day 1 b	Bim SR Cycle 1 Day 1	Bim SR Cycle 1 Day 1
Bim SR Cycle 1 Day 2 b	Bim SR Cycle 1 Day 1 + 1	Bim SR Cycle 1 Day 1 + 1
Week 4/Cycle 1 Week 4 b	25	[Bim SR Cycle 1 Day 1+ 2, 38]
Week 8/Cycle 1 Week 8 b	53	[39, 66]
Week 12/Cycle 1 Week 12 b	81	[67, 91]
Week 15/Cycle 1 Week 15 b	102	[92, Bim SR Cycle 2 Day 1- Bim SR Cycle 1 Day 1]
Week 16/Bim SR Cycle 2 Day 1 c	1	Bim SR Cycle 2 Day 1
Cycle 2 Day 2 c	2	Bim SR Cycle 2 Day 1 + 1
Week 20/Cycle 2 Week 4 c	29	[Bim SR Cycle 2 Day 1+ 2, 42]
Week 24/Cycle 2 Week 8 c	57	[43, 70]
Week 28/Cycle 2 Week 12 c	85	[71, 95]
Week 31/Cycle 2 Week 15 c	106	[96, Bim SR Cycle 3 Day 1- Bim SR Cycle 2 Day1]
Week 32/Bim SR Cycle 3 Day 1 d	1	Bim SR Cycle 3 Day 1
Cycle 3 Day 2 d	2	Bim SR Cycle 3 Day 1 + 1
Week 36/Cycle 3 Week 4 d	29	[Bim SR Cycle 3 Day 1+ 2, 42]
Week 40/Cycle 3 Week 8 d	57	[43, 70]
Week 44/Cycle 3 Week 12 d	85	[71, 95]
Week 47/Cycle 3 Week 15 d	106	[96, 123]
Week 52/Cycle 3 Week 20 d	141	>=124

a Relative to the date of the SLT treatment.

b Relative to the date of Bim SR 1st implant. If a patient did not receive the first Bim SR cycle, but treated in SLT at Day 1, Bim SR cycle 1 Day 1 will be determined as SLT+ 3 days.

c Relative to the date of Bim SR 2nd implant.

d Relative to the date of Bim SR 3rd implant.

